13.2.4 CONJUNCTIVAL REDNESS

The Ora Calibra® Conjunctival Redness Scale for Dry Eye will be performed on all scheduled visits. The conjunctival redness scale ranges from [REDACTED]

Conjunctival redness scores will be summarized and analyzed by visit as described in [section 13.2.1](#).

13.2.5 UNANESTHETIZED SCHIRMER'S TEST

Unanesthetized Schirmer's Test will be assessed on both eyes at Day -14, Day 1, Day 15, Day 29, and Day 57. The Schirmer's test strip will be placed in the lower temporal lid margin of each eye. After 5 minutes, the test strip will be removed and the length of the moistened area will be recorded in millimeters (mm) for each eye. Lower values indicate less tears produced in the eye.

Unanesthetized Schirmer's Test will be summarized and analyzed for the study eye by visit as described in [section 13.2.1](#).

Sample means of the unanesthetized Schirmer's test scores in the study eye will be displayed graphically in a line chart with SE bars by visit and treatment group.

13.2.6 TEAR FILM BREAK-UP TIME

Tear film break-up time will be measured at all scheduled visits on all scheduled visits in both eyes. For each eye, two measurements will be recorded in seconds and averaged unless the two measurements are > 2 seconds apart and are each < 10 seconds, in which case, a third measurement will be taken and the two closest of the three will be averaged and used for analyses. If the differences between two sequential pairs of measurements are the same (e.g., 3, 6, 9 seconds), then the median of the three readings will be used for analysis.

Tear film break-up time will be summarized and analyzed for the study eye by visit as described in [section 13.2.1](#).

13.2.7 VISUAL ANALOG SCALE OF OCULAR DRYNESS

At each visit, subjects will be asked to rate each ocular symptom due to ocular dryness by placing a vertical mark on the horizontal line to indicate the current level of discomfort. 0% corresponds to "no discomfort" and 100% corresponds to "maximal discomfort." Subjects are to evaluate their current ocular discomfort symptoms as experienced while completing the questionnaire. Reported symptoms include burning/stinging, itching, foreign body sensation, blurred vision, eye dryness, photophobia, and pain.

Visual analog scale will be summarized and analyzed by visit and symptom as described in [section 13.2.1](#).

Sample means of the VAS symptoms will be displayed graphically in a line chart with SE bars by visit and treatment group for each symptom separately.

13.2.8 OCULAR SURFACE DISEASE INDEX[®]

The OSDI[®] is assessed on a scale of 0 to 100, with higher scores representing greater disability. The OSDI[®] asks the following 12 questions at the subject level:

Have you experienced any of the following during the last week?

- 1) Eyes that are sensitive to light?
- 2) Eyes that feel gritty?
- 3) Painful or sore eyes?
- 4) Blurred vision?
- 5) Poor vision?

Have problems with your eyes limited you in performing any of the following during the last week?

- 6) Reading?
- 7) Driving at night?
- 8) Working with a computer or bank machine (ATM)?
- 9) Watching TV?

Have your eyes felt uncomfortable in any of the following situations during the last week?

- 10) Windy conditions?
- 11) Places or areas with low humidity (very dry)?
- 12) Areas that are air conditioned?

OSDI[®] will be assessed at each visit at the subject level. The 5-unit scale for responses to the OSDI[®] is given by the following:

The total OSDI[®] score is calculated by the following:

$$\text{OSDI}^{\circledast} = \frac{(\text{Sum of Scores}) \times 25}{\text{_____}}$$

of Questions Answered

Note that the number of questions answered in the denominator should exclude those questions with a response of "N/A."

OSDI® will be summarized and analyzed by visit and by question, subgroup, and total score as described in [section 13.2.1](#).

13.2.9 ORA CALIBRA® OCULAR DISCOMFORT SCALE

Ocular discomfort scores will be subjectively graded by the subjects using the Ora Calibra® Ocular Discomfort Scale at all scheduled visits. The ocular discomfort scale ranges from [REDACTED]

Ocular Discomfort Scale will be summarized and analyzed by visit as described in [section 13.2.1](#).

Sample means of the Ocular Discomfort Scale scores in the study eye will be displayed graphically in a line chart with SE bars by visit and treatment group.

13.2.10 ORA CALIBRA® OCULAR DISCOMFORT & 4-SYMPOTM QUESTIONNAIRE

Ocular discomfort and dry eye symptoms will be assessed at all scheduled visits at the subject level in regard to how both eyes feel. The Ora Calibra® Ocular Discomfort & [REDACTED]

Ocular Discomfort & 4-Symptom Questionnaire will be summarized and analyzed by visit as described in [section 13.2.1](#).

Sample means of the symptoms from the Ocular Discomfort & 4-Symptom Questionnaire will be displayed graphically in a line chart with SE bars by visit and treatment group for each symptom separately.

14. Summary of Efficacy Analyses

A summary of all efficacy analyses will be presented. For MMRM models, treatment group LS means, LS mean differences, SEs for the LS mean differences, and p-values for the treatment group comparisons will be presented. For t-tests, treatment group sample means, sample mean differences, SEs for sample mean differences, and p-values for treatment group comparisons will be presented.

15. Safety Analyses

All safety analyses will be conducted using the Safety population.

15.1 Adverse Events

An AE is defined as any untoward medical occurrence associated with the use of IP in humans, whether or not considered IP-related. An AE can be any unfavorable and unintended sign (e.g., an abnormal laboratory finding), symptom, or disease temporally associated with the use of an IP, without any judgment about causality. An AE can arise from any use of the IP (e.g., off-label use, use in combination with another drug or medical device) and from any route of administration, formulation, or dose, including an overdose. All AEs will be coded using MedDRA Version 24.0.

Treatment-emergent adverse events (TEAEs) are defined as any event that occurs or worsens on or after the day that randomized study treatment is initiated.

An overall summary will be presented that includes the number of AEs, TEAEs, SAEs, treatment-emergent serious adverse events (TE-SAEs), number of subjects with TEAEs by maximum severity, and number of subjects with TEAEs by relationship to study drug. The summary will also include the number and percentage of subjects with treatment discontinuation due to an AE, the number and percentage of subjects with an AE resulting in death, and the number and percentage of subjects who experienced at least one AE, TEAE, SAE, and TE-SAE by treatment group and for all subjects. This summary will include breakdowns of AEs and TEAEs further categorized as ocular or non-ocular as well as the number and percentage of resolved ocular AEs and the mean and SD number of days until AE resolution for resolved ocular AEs.

Additional summaries of TEAEs will be provided showing the number and percentage of subjects who experienced at least one TEAE. These summaries will be presented by SOC and PT. Non-ocular TEAEs will be summarized using discrete summary statistics and presented by treatment group at the subject and event level by SOC and PT. Ocular TEAEs will be similarly summarized at the subject and event level by SOC and PT. If a subject reports the same PT multiple times within the same SOC, that PT will only be reported once within that SOC. As with the PT, if a subject reports multiple conditions within the same SOC, that SOC will only be reported once. In the summary, SOC will be listed in order of descending frequency for all subjects; PTs will be listed in order of descending frequency for all subjects within each SOC.

Conjunctivitis AEs will also be summarized by number of AEs and number and percentages of subjects who experienced at least one conjunctivitis AE. Categories of conjunctivitis AEs (bacterial, viral, and hypersensitivity) will be further summarized as described. Additionally, the number of subjects with a conjunctivitis AE that experience any of the following symptoms will be summarized:

- Injected Sclera
- Redness
- Burning
- Eye Discharge
- Unusual Crusting on Eye When Awakening

- Ocular Itchiness
- Nasal Itchiness
- Sneezing
- Excessive Tearing
- Other Signs or Symptoms.

A subject listing of conjunctivitis AEs will be generated for all randomized subjects.

Additionally, separate summaries will be provided for the following categories of AEs:

- Ocular AEs
- Non-ocular AEs
- Ocular TEAEs
- Non-ocular TEAEs
- Ocular treatment-related TEAEs
- Non-ocular treatment-related TEAEs
- SAEs

Severity of an AE is defined as a qualitative assessment of the degree of intensity of an AE as determined by the Investigator or reported to him/her by the subject. The assessment of severity is made irrespective of relationship to study drug or seriousness of the event and should be evaluated according to the following scale:

- *Mild*: Event is noticeable to the subject, but is easily tolerated and does not interfere with the subject's daily activities.
- *Moderate*: Event is bothersome, possibly requiring additional therapy, and may interfere with the subject's daily activities.
- *Severe*: Event is intolerable, necessitates additional therapy or alteration of therapy, and interferes with the subject's daily activities.

Summaries of TEAEs by maximal severity will be presented for ocular AEs and non-ocular AEs separately. The number of subjects with any TEAEs (along with percentages) will be tabulated by SOC and PT within each SOC by treatment group. To count the number of subjects with any TEAEs, if a subject has multiple TEAEs coded to the same PT within the same SOC, the subject will be counted once under the maximal severity.

The occurrence of non-ocular and ocular TEAEs will also be tabulated by SOC, PT, and study day of onset (prior to Day 9, Day 9 to Day 29, After Day 29).

The relationship of each AE to the IP should be determined by the investigator (in a masked manner) using these explanations:

- **Suspected:** A reasonable possibility exists that the IP caused the AE. A suspected AE can be further defined as:
 - *Definite:* Relationship exists when the AE follows a reasonable sequence from the time of IP administration, follows a known response pattern of the drug class, is confirmed by improvement on stopping the IP and no other reasonable cause exists.
 - *Probable:* Relationship exists when the AE follows a reasonable sequence from the time of IP administration, follows a known response pattern of the drug class, is confirmed by improvement on stopping the IP and the suspect IP is the most likely of all causes.
 - *Possible:* Relationship exists when the AE follows a reasonable sequence from the time of administration, but could also have been produced by the subject's clinical state or by other drugs administered to the subject.
- **Not Suspected:** A reasonable possibility does not exist that the IP caused the AE. A not suspected AE can further be defined as:
 - *Not Related:* Concurrent illness, concurrent medication, or other known cause is clearly responsible for the AE, the administration of the IP and the occurrence of the AE are not reasonably related in time, OR exposure to IP has not occurred.

All possible, probable, and definite TEAEs are considered as treatment-related TEAEs.

All AEs will be presented in a subject listing for all screened subjects. Separate listings will be produced for Conjunctivitis AEs, SAEs, AEs leading to treatment discontinuation, and AEs leading to death for all randomized subjects.

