8.8 Study Duration

An individual subject's participation will involve at least 6 visits over approximately a 10-week (~70 days) period (56 days of treatment and 14 days pre-screening).

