10.4.7 Safety Variables

Adverse events will be coded using the MedDRA dictionary. Frequencies and percentages of subjects with treatment-emergent adverse events (TEAEs), serious TEAEs, and TEAEs causing premature discontinuation will be provided by treatment group. An AE is treatment emergent if it 1) occurs after the first dose of randomized study treatment or 2) if it is present prior to receipt of randomized study treatment but worsens in severity or increases in frequency after the first dose of randomized study treatment. Furthermore, frequencies will be given of subjects with TEAEs by system organ class and preferred term; by system organ class, preferred term and maximal severity; by system organ class, preferred term for treatment-related AEs; by system organ class and preferred term for SAEs; and by system organ class, preferred term, and day of onset. Separate analyses will be performed for ocular specific and all AEs (including systemic).

Other safety endpoints including visual acuity, slit-lamp biomicroscopy, dilated fundoscopy, and intraocular pressure will be summarized by treatment group and visit using descriptive statistics. Changes or shifts from baseline will also be summarized where appropriate. For assessments performed by eye, study eye and fellow eye will be summarized separately. In addition, shifts from baseline to worst on-treatment value for ocular safety assessments will be summarized. All safety endpoints will be assessed using the Safety population.

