8.4 Data Analysis Conventions

All data analyses will be performed after the study is completed and the database has been locked and released for unmasking. Statistical programming and analyses will be performed using SAS® Version 9.4 or higher. Output will be provided in RTF (rich text format) for tables, listings, and figures using landscape orientation. All study data will be listed by subject, treatment, and visit (as applicable) based on all enrolled subjects unless otherwise specified.

All summaries will be presented by treatment group and visit where appropriate, unless otherwise specified. Listings will be presented for all data collected on the eCRFs, sorted by subject id number and visit.

Summaries for continuous and ordinal variables will include the number of observations (n), arithmetic mean, SD, median, minimum, and maximum. Minima and maxima will be reported with the same precision as the raw values; means and medians will be presented to one additional decimal place than reported in the raw values. Standard deviations will be presented to two additional decimal places than reported in the raw values. Summaries for discrete variables will include frequency counts and percentages. All percentages will be rounded to one decimal place (i.e., XX.X%).

All statistical tests will be two-sided with a significance level of 0.05 ($\alpha = 0.05$) unless otherwise specified. Confidence intervals (CI) will be two-sided at 95% confidence levels where appropriate. All p-values will be rounded to four decimal places; p-values less than 0.0001 will be presented as "<0.0001"; p-values greater than 0.9999 will be presented as ">0.9999."

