[REDACTED]  
LSMEANS TREATMENT / CL PDIFF;  
RUN;
```

25. Appendix 2

Schedule of Visits and Assessments

Procedure	Screening Visit 1 (Day -14 ± 2)	Baseline Visit 2 (Day 1)	Visit 3 (Day 8 ± 1)	Visit 4 (Day 15 ± 2)	Visit 5 (Day 29 ± 2)	Visit 6 (Day 57 ± 3)	Visit 7-9 ⁴
Informed Consent / HIPAA	X						
Medical / Medication History and Demographics	X						
Placebo Run-In Collection		X					
Study Drug Collection			X	X	X	X	
Medical / Medication Update		X	X	X	X	X	X
Pregnancy Test	X ²					X ²	
Ocular Discomfort Scale	X	X	X	X	X	X	
Ocular Discomfort & 4-Symptom Questionnaire	X	X	X	X	X	X	
VAS	X	X	X	X	X	X	
OSDI® Questionnaire	X	X	X	X	X	X	
Visual Acuity (ETDRS)	X	X	X	X	X	X	
Slit Lamp Biomicroscopy	X	X	X	X	X	X	
Conjunctival Redness	X	X	X	X	X	X	
TFBUT	X	X	X	X	X	X	
Fluorescein Stainng	X	X	X	X	X	X	
Lissamine Green Staining	X	X	X	X	X	X	
Schirmer's Test	X	X		X	X	X	
Intraocular Pressure	X					X	
Dilated Fundus Exam	X					X	
Review of Qualification Criteria	X	X					

Placebo Run-In Dispensation and Instillation	X						
Blood Sampling for Immunogenicity		X			X	X	X
Randomization		X					
Study Drug Instillation		X	X				
Drop Comfort Scale		X	X				
Drop Comfort Questionnaire		X	X				
Adverse Event Query	X	X	X	X	X	X	X
Study Drug Dispensation		X ¹	X	X	X		
Exit Subject from Study						X ³	

¹ The Visit 2 study drug kit is re-dispensed at Visit 3 (as each kit includes 2-week supply of study drug).

² To women of child-bearing potential.

³ For subjects with negative immunogenicity results at Visit 6.

⁴ Subjects will be asked to return for Blood Sample for Immunogenicity Testing if they test positive for immunogenicity at Visit 6. Visit 7 will occur approximately 6-12 months after Visit 6. If subject tests positive for immunogenicity at Visit 7, they will be asked to return for Visit 8 approximately 12 months after Visit 7. If subject tests positive for immunogenicity at Visit 8, subject will be asked to return for Visit 9 approximately 12 months after Visit 8.

Certificate Of Completion

Envelope Id: 0FD96C8D49AC44D78A4A23EF3B2091D1 Status: Completed

Subject: Complete with DocuSign: HanAll HL036-DED-US-P302 Statistical Analysis Plan Draft V1.0 23-JAN-20...

Source Envelope:

[figure not shown]
Document Pages: 45 Signatures: 3

Certificate Pages: 5 Initials: 0

AutoNav: Enabled

Enveloped Stamping: Disabled

Time Zone: (UTC-05:00) Eastern Time (US & Canada)

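### The TEAE definition has no end date, and only subjects antibody-positive at Visit 6 have scheduled adverse event queries after that visit, so off-drug events from a selected subgroup can enter the between-arm safety tables

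*SAP*

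**What the plan says.** **Definition of a TEAE.** SAP 15.1: "Treatment-emergent adverse events (TEAEs) are defined as any event that occurs or worsens on or after the day that randomized study treatment is initiated". Protocol 10.4.7 is also open at the far end: an event qualifies if it "occurs after the first dose of randomized study treatment", or if it was present earlier and then worsens. The SAP 15.1 table by day of onset closes with an unbounded category that starts after Day 29.

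**Who is followed after Visit 6.** In the SAP Appendix 2 schedule, the exit mark at Visit 6 carries footnote 3: "For subjects with negative immunogenicity results at Visit 6". Footnote 4 covers the others: "Subjects will be asked to return for Blood Sample for Immunogenicity Testing if they test positive for immunogenicity at Visit 6". On timing it says "Visit 7 will occur approximately 6-12 months after Visit 6"; if still positive, "they will be asked to return for Visit 8 approximately 12 months after Visit 7"; and Visit 9 follows after about another 12 months on the same condition. The adverse event query row is marked in the Visit 7-9 column.

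**When the tables are made.** SAP 8.4: "All data analyses will be performed after the study is completed and the database has been locked and released for unmasking". SAP 17 plans no interim analysis. Protocol 11.6 locks Visit 1-6 data once the last randomized subject completes Visit 6, and then mentions a later final lock. The protocol synopsis refers to an interim lock and unmasking.

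**Planned duration.** Protocol 8.8: "An individual subject's participation will involve at least 6 visits over approximately a 10-week (~70 days) period". Visits 7-9 are not in SAP Table 1, and SAP 15.6 describes sampling only at Days 1, 29 and 57.

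**The concern.** The safety objective is to compare an eight-week treatment with placebo. That comparison is fair when both arms are asked about adverse events over the same planned period. Here the period depends on an antibody result obtained after randomization, which exposure to the active protein can cause and which the placebo, containing no tanfanercept (protocol 7.1.3), should not. The tables report numbers and percentages of subjects by arm, and no adjustment for follow-up time is planned. If the late events are counted, the arm with more antibody-positive subjects will show more events even when the drug has no effect on them.

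The same gap reaches two neighbouring calculations. SAP 12.1 and 12.2 count expected doses and days of exposure from Day 1 to study completion or discontinuation. If an antibody-positive subject completes the study at Visit 7 or later, both quantities include months without treatment.

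**Working it through.** The plan gives no figure to reproduce on this point. The check has four parts.

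**1. Does anything in the visible text close the window?**
- SAP 15.1 and protocol 10.4.7: start only.
- SAP 3.1, Table 1: the Visit 6 analysis window ends at Day 60, but the windows are stated to apply to efficacy only.
- Protocol 9.5: follow-up of unresolved events, and of newly identified events judged potentially related, for up to 30 days after the last visit. This is a follow-up rule. It does not define which events are tabulated.
- Protocol 11.6: a Visit 1-6 lock, not linked to any table. SAP 1 says its statistical methods supersede those in the protocol, and SAP 8.4 names no Visit 6 cut-off.
- SAP 21: the conjunctivitis, all-ocular, all-non-ocular and SAE tables cover all events, so even the TEAE start date does not apply to them.

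Nothing found closes it.

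**2. Length of follow-up** (SAP Appendix 2, footnote 4; 30.4375 days per month)
- After Visit 6: shortest 6 + 12 + 12 = 30 months; longest 12 + 12 + 12 = 36 months.
- Day 1 to Visit 7: 57 + 183 = 240 days up to 57 + 365 = 422 days, or 4.2 to 7.4 times the 57 days of an antibody-negative completer.
- Day 1 to Visit 9: 57 + 913 = 970 days up to 57 + 1,096 = 1,153 days, or 17 to 20 times, with 94-95% of it off drug.

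**3. Illustrative size with no drug effect on adverse events.** Assumptions: a constant event rate on and off treatment; a proportion p of subjects with any TEAE by Day 57; every antibody-positive subject returns and reports fully. Antibody-positive proportions are a (active) and b (placebo), and f is the extra days.

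- Risk by day 57 + f: P(f) = 1 − (1 − p)^((57 + f)/57)
- Spurious arm difference: (a − b) × [P(f) − p]

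Worked case: p = 20%, a = 10%, b = 2%, f = 365. P = 1 − 0.8^(422/57) = 80.8%. Difference = 0.08 × (80.8% − 20%) = 4.9 points (26.1% v 21.2%).

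Spurious difference in percentage points at 6 / 12 / 36 months of extra follow-up:

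| a v b | p = 10% | p = 20% | p = 30% |
|---|---|---|---|
| 2% v 0% | 0.5 / 0.9 / 1.6 | 0.8 / 1.2 / 1.6 | 1.0 / 1.3 / 1.4 |
| 5% v 1% | 1.0 / 1.8 / 3.1 | 1.6 / 2.4 / 3.2 | 1.9 / 2.5 / 2.8 |
| 10% v 2% | 2.1 / 3.5 / 6.3 | 3.3 / 4.9 / 6.3 | 3.8 / 5.0 / 5.6 |
| 20% v 2% | 4.6 / 7.9 / 14.1 | 7.4 / 11.0 / 14.2 | 8.6 / 11.3 / 12.6 |
| 10% v 10% | 0 | 0 | 0 |

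**4. Compliance and exposure.** Under SAP 12.1, a subject who completes at Day 57 has 2 × 57 = 114 expected doses. If completion is Visit 7, the figure is 2 × 240 = 480 to 2 × 422 = 844. A fully adherent subject, having taken 112 to 114 doses, would score between 112/844 = 13% and 114/480 = 24%, and would be classed as under-compliant (below 80%). SAP 12.2 would show 240 to 422 days of exposure for eight weeks of treatment.

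**The case against.** **The Visit 1-6 lock may already exclude these events.** Protocol 11.6 provides for it, the synopsis mentions an interim lock, and no passage plans tables that pool Visits 7-9. This stands as far as it goes: one cannot say that the tables will contain late events. But no document ties the tables to that lock, and a programmer applying SAP 15.1 and 8.4 literally would include them.

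**Visits 7-9 appear only in SAP Appendix 2.** The protocol's Visit 6 is a study exit with no antibody condition in the visible text, and its Appendix 1 has only an optional blood-sample visit. Whether that column carries an adverse event query cannot be read with certainty from the extracted table. Text beside the immunogenicity sampling entries is redacted, and a rule for late events may be there. This stands as a limit on the check. It also means the two schedules, as visible, need reconciling.

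**The size is assumed.** True. No antibody rate is given. Protocol 1 reports blood concentrations below the quantitation limit in all samples, which lends no support to high antibody rates but does not exclude them. The model also assumes an unchanged event rate off drug, full recall and full return, and the 36-month figures require every positive subject to remain positive through Visit 8.

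**Readings that go too far.** A reader might infer that the extra events fall almost entirely in the active arm. That is plausible, but placebo subjects who test positive would be followed too, and no rate by arm is stated. A reader might infer a false link between antibodies and adverse events, but no table of adverse events by antibody status is planned. A reader might also infer that masked causality assessment is lost for late events. That requires unmasking before Visits 7-9, whereas reading SAP 8.4 as deferring all analysis to study completion implies none. Both could hold only with a second set of tables, which neither document plans.

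**Conclusion.** The concern holds as a bias that the SAP permits, not one that is certain to occur. Three stated features combine: no end to the TEAE window, scheduled queries after Visit 6 only for antibody-positive subjects, and no statement of which lock supplies the adverse event tables. Read literally, the SAP lets the period of adverse event collection depend on a result that treatment can cause.

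The direction would be against whichever arm has more antibody-positive subjects. Over assumed 8-week risks of 10% to 30% and assumed antibody rates of 2% to 20% (active) against 0% to 2% (placebo), the spurious difference runs from about 0.5 to 14 points. If follow-up ends at Visit 7, it runs from 0.5 to 11.3 points. It is zero if antibody rates are equal or if the tables use Visit 1-6 data only.

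The adverse event tables are descriptive, and the primary efficacy endpoints are untouched. The point should still be settled before unmasking, because safety is part of the stated objective and readers will compare the arm percentages.

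**What to change.** 1. In SAP 15.1, end the TEAE window and the category after Day 29 at one point defined alike for all subjects: Visit 6/early termination, or a uniform 30 days after it. Apply the same limit to the SAE, conjunctivitis and all-event tables, which do not use the TEAE definition.
2. List adverse events from Visits 7-9 separately, outside the between-arm tables.
3. Name the Visit 1-6 lock of protocol 11.6 as the source of the adverse event tables, and align SAP 8.4 with it. If the 30-day option is chosen, state that the lock also holds those 30 days for every subject.
4. For SAP 12.1 and 12.2, define the completion date as Visit 6/early termination, whatever the antibody result.
5. Reconcile SAP Appendix 2 with SAP Table 1, SAP 15.6, protocol 8.8 and protocol Appendix 1 on what happens after Visit 6.

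The cost is a few sentences in the SAP, one date condition in the adverse event programs and one extra listing. No data are lost. With a common end point the planned windows are equal, and the artificial difference computed above becomes zero.
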